## 12.2.5 Complaint Reporting

The Abre system is CE marked and obtained FDA approval in October 2020. All product complaints must be reported for Post Market Surveillance. The reporting of product complaints is not part of the clinical study and should be done in addition to the Adverse Event reporting requirements.

- **Product Complaint:** Any written, electronic or oral communication that alleges deficiencies related to the identity, quality, durability, reliability, safety, effectiveness or performance of a medical device that has been placed on the market.
- **Vigilance and Medical Device Reporting:** A system used to notify the regulatory body about incidents with regard to medical devices that carry the CE mark or are FDA approved. This system requires a manufacturer to notify the regulatory body of incidents immediately on learning of them.
- **Incident:** Any malfunction or deterioration in the characteristics and/or performance of a device, as well as any inadequacy in the labeling or the instructions for use which, directly or indirectly, might lead to or might have led to the death of a subject, or user or of other persons or to a serious deterioration in their state of health.

It is the responsibility of the investigator to report all product complaint(s) associated with a medical device distributed by Medtronic regardless whether they are related to intended use, misuse, or abuse of the product. Reporting must be done within 48 hours and per the regular channels for market released products.

## 12.2.6 Emergency Contact Details for Reporting Events and Device Deficiencies

In case of an immediately reportable Adverse Event or in a medical emergency situation, the investigator can contact the Medtronic Study Manager or designee. Contact details of Medtronic Study Management are subject to change and will be maintained in the Investigational Site File and updated contact details will be provided to sites whenever applicable.

# 13 Committees / Core Laboratories

## 13.1 Data Safety Monitoring Board

A Data Safety Monitoring Board (DSMB) is composed of at least four members with pertinent expertise (3 physicians and at least 1 biostatistician) who are not participants or directly involved in the conduct of the study. A minimum of one interventionalist will serve as a member of the DSMB.

The responsibility of the DSMB is to evaluate safety data during the course of the study and to advise Medtronic about the continuing safety of the study, to ensure the well-being of the current participants and those yet to be enrolled as well as the continuing validity and scientific merit of the study.

Based on the safety data, the DSMB may recommend that Medtronic modify or stop the study. DSMB composition, duties, procedures, deliberation rules are detailed and documented in the DSMB Charter.

The Data Safety Monitoring Board will be established and led by:

Syntax  
[name]  
[name]  
New York, New York 10006, USA  
[contact]  
[contact]

## 13.2 Clinical Events Committee

The Clinical Events Committee (CEC) is made up of clinicians (interventional and non-interventional) with pertinent expertise (i.e. vascular surgeons, interventional radiologists) who are not participants in the study and who do not have any other real or potential conflicts of interest. The CEC is charged with the categorization of selected adverse events and clinical endpoints in the study, using criteria established at the outset of the study and specified by the CIP, the CEC Manual of Operations, and relevant societal reporting standards. The CEC Manual of Operations will specify explicit rules outlining the minimum amount of data required and the algorithm followed in order to classify an event.

Database automated alerts and the independent Medical Monitor at Medtronic's designated Contract Research Organization (CRO) will identify clinical events requiring adjudication as specified in the CEC Manual of Operations. The CEC will regularly evaluate and adjudicate these events, as well as other events as may be requested by Medtronic.

The CEC will be established and led by:

Syntactx  
[name]  
[name]  
New York, New York 10006, USA  
[contact]  
[contact]

### 13.3 Duplex Ultrasound Core Laboratory

The Duplex Ultrasonography Core Laboratory (Duplex Core laboratory) is responsible for developing protocol requirements, reviewing DUS exams, interpreting subject DUS data, and providing feedback on the quality of the DUS exams to participating sites. The Duplex Core laboratory will review, analyze, and record data on the Duplex Core laboratory Assessment eCRF. The Duplex Core laboratory's reviewer's interpretation of all DUS exams will be used for the data analyses. All DUS exams will be evaluated by:

VASCORE  
The Vascular Ultrasound Core Laboratory  
[name]  
Boston, MA 02114, USA  
[contact]  
[contact]

### 13.4 Venography, X-ray, and IVUS Core Laboratory

The venography, X-ray, and IVUS Core Laboratory is responsible for developing protocol requirements, reviewing and interpreting venograms; X-ray, and IVUS studies, and providing feedback on the quality of the imaging studies to participating sites. The core laboratory will review, analyze, and record data on the applicable Core laboratory assessment eCRF. The core laboratory's reviewer's interpretation of all imagings will be used for the data analyses. All venogram, X-ray, and IVUS recordings will be evaluated by:

Syntactx  
[name]  
[name]  
New York, New York 10006, USA  
[contact]  
[contact]

## 14 Statistical Design and Methods

This section outlines the statistical design and methods set at the start of the study, and statistical methods for post-approval study phase. Primary endpoint and study success criteria has been added in the below corresponding sections. The clinical performance of the Abre system will be evaluated through a prospective, single-arm, non-randomized, multi-center, global clinical study in a total of 200 included subjects with a hypothesis-based 30-day composite safety endpoint and a hypothesis-based 12-month effectiveness endpoint assessed by performance goals.

Statistical analysis will be performed by Medtronic statisticians or their designated representatives. A separate Statistical Analysis Plan (SAP) has been developed to further describe pre-specified statistical methods, data handling rules, and analyses that will be employed. Any deviation from the original statistical analysis plan will be reported in the final study report, along with justification for the deviation(s).

One-sided statistical tests will have p-values less than 0.025 deemed significant while two-sided tests will have p-values less than 0.05 deemed significant. Statistical analyses will be conducted in SAS version 9.4 or above (SAS Institute, Cary, N.C.) or another validated statistical software package.

For adverse event reporting, the primary analysis will be based on subject counts, not event counts. Both subject counts and event counts will be presented in tabular summaries of results, as appropriate.

### 14.1 Performance Goals

#### 14.1.1 Performance Goal: Primary Effectiveness Endpoint

The primary effectiveness performance goal endpoint in the study is primary patency. The statistical hypothesis on this endpoint is that primary patency through 12 months will exceed a performance goal established from historical literature references using venous stenting as the treatment of choice. Formally, the null and alternative hypotheses to be tested appear below:

$$H_0: \pi \leq PG$$

$$H_A: \pi > PG$$

Where  $\pi$  is the primary patency at 12 months in the study population and PG is the performance goal, which is calculated as follows. An extensive and independent review of the available literature produced references on venous stenting in similar patient populations. These data are derived from published studies of venous stenting which measured target vessel patency as an endpoint. In order to estimate the expected rate of primary patency in the study population at 12 months, the review of the available literature was used (see Appendix A Scientific Literature Search).

Based on the literature, the weighted mean expected primary patency was 85.7%. By subtracting a margin of indifference of 10% from expected performance (85.7% - 10% = 75.7%); consequently, the value of 75% is therefore taken as the performance goal for the current study.

For analysis of the imaging component of primary patency, if a subject has both a valid venogram and DUS during the 12-month follow-up period then the venogram will be used. If no venogram is available, then the DUS will be used.

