## 14.2 Sample Size Calculation

**Primary Effectiveness:** Using the assumptions above on the performance goal and anticipated outcome, we assume desired power of at least 92% under difference testing relative to the performance goal at a one-sided alpha of 0.025. The resulting evaluable sample size required is then 160 subjects using exact binomial test for a single proportion. Accounting for attrition during follow-up, the sample size is augmented by 20% to 200 subjects. Every effort will be made, however, to minimize loss to follow-up.

**Primary Safety:** Using the assumptions above on the performance goal and anticipated outcome, we assume desired power of at least 92% under difference testing relative to the performance goal at a one-sided alpha of 0.025. The resulting evaluable sample size required is then 193 subjects using exact binomial test for a single proportion. Accounting for attrition during follow-up, the sample size is augmented by 3.5% to 200 subjects. Every effort will be made, however, to minimize loss to follow-up.

In summary, the overall power of the study is at least 84% while the effectiveness and safety performance goals are as follows:

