**Table VI. Number of publications with patients and limbs by indication**

Clinical Category	Series	Patients	Limbs
Acute	22 (32%)	662 (16.8%)	674 (15.9%)
Post-thrombotic	18 (26%)	1,092 (27.7%)	1,185 (27.9%)
Non-thrombotic	6 (9%)	787 (20.0%)	865 (20.4%)
Mixed, Acute & Chronic 	14 (21%)	620 (15.7%)	639 (15.0%)
Mixed; PT and NT	8 (12%)	782 (19.8%)	884 (20.8%)
All Series	68	3,943	4,247

*PT= post-thrombotic; NT= non-thrombotic.*

*Individual percentages may not add to 100% due to rounding*

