**Table XIII. Patency rates at 12 months after iliofemoral venous stenting**

Clinical Category (Limbs)	12-Month Patency Rates		
	Primary	Primary-Assisted	Secondary
Acute (N = 662)	84.0%	91.1%	96.7%
Post-thrombotic (N = 1,175)	80.5%	88.1%	91.9%
Non-thrombotic (N = 901)	94.8%	100.0%	100.0%
Mixed, Acute & Chronic (N = 649)	83.6%	85.0%	93.6%
Mixed; PT and NT (N = 958)	83.8%	92.9%	89.5% 
All Stent Publications (N = 4,247)	85.7%	93.8%	95.2%

 Secondary patency for this cohort is lower than primary-assisted patency since different series are included in the two measures.

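### The 85.7% planning rate for 12-month primary patency cannot be reproduced from Appendix A; the printed tables give 85.1–85.5%, at which effectiveness power is about 89–92%, not at least 92%

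*Protocol*

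**What the plan says.** Protocol 14.1.1 gives the planning rate: "Based on the literature, the weighted mean expected primary patency was 85.7" per cent. It subtracts a 10-point margin to reach 75.7% and then states "consequently, the value of 75% is therefore taken as the performance goal for the current study". SAP 6.1 and 7.9.1.2 repeat both steps. The 85.7% appears in Appendix A as the weighted average at the foot of Table IV and as the overall row of Table XIII, "All Stent Publications (N = 4,247" limbs).

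On power, protocol 14.2 says "we assume desired power of at least 92% under difference testing relative to the performance goal at a one-sided alpha of 0.025" and "The resulting evaluable sample size required is then 160 subjects using exact binomial test for a single proportion". The safety endpoint has the same 92% floor with 193 evaluable subjects. The section closes with "In summary, the overall power of the study is at least 84" per cent. The power output in SAP 6.3 uses 0.8570 as the alternative and reports 0.9288 for effectiveness (pass at 131 or more of 160) and 0.9233 for safety (pass at 15 or fewer of 193). The protocol synopsis and the SAP introduction set a lower requirement of 80% overall power.

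**The concern.** Table VI ("Number of publications with patients and limbs by indication") and Table XIII divide the same literature into five categories that do not overlap. An overall weighted mean must therefore equal the weighted mean of the five category rates. The printed category rates do not average to 85.7% under any set of counts that the appendix prints, and the row counts in Table XIII do not sum to its total.

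The rate matters in two places. It is the starting point for the performance goal, and it is the alternative in the effectiveness power calculation. The effectiveness floor is only 0.9 percentage points below the computed power (92% against 92.88%), so a shift of a few tenths of a point in the planning rate is enough to break it.

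**Working it through.** **1. The plan's own figures, from its own inputs.** Exact binomial:
- Effectiveness, N = 160, goal 0.75, alternative 0.857: P(X ≥ 131 | 0.75) = 0.0247 and P(X ≥ 131 | 0.857) = 0.9288. Both match SAP 6.3.
- Safety, N = 193, goal 0.125, alternative 0.056: P(X ≤ 15 | 0.125) = 0.0249 and P(X ≤ 15 | 0.056) = 0.9233. Both match.
- Overall: 0.9288 × 0.9233 = 0.8575 if the endpoints are independent, and 0.9288 + 0.9233 − 1 = 0.8521 as a lower bound without that assumption. The stated 84% equals 0.92 + 0.92 − 1.

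The power run is correct for its inputs. Only the source of the 0.857 is in question.

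**2. Inputs for the rate (Appendix A).**

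| Category | Table XIII rate | Table XIII N | Table VI limbs | Table VI patients |
|---|---|---|---|---|
| Acute | 84.0% | 662 | 674 | 662 |
| Post-thrombotic | 80.5% | 1,175 | 1,185 | 1,092 |
| Non-thrombotic | 94.8% | 901 | 865 | 787 |
| Mixed, acute and chronic | 83.6% | 649 | 639 | 620 |
| Mixed, post- and non-thrombotic | 83.8% | 958 | 884 | 782 |
| Sum of rows | | 4,345 | 4,247 | 3,943 |
| Printed total | 85.7% | 4,247 | 4,247 | 3,943 |

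**3. Weighted means, Σ(N × rate) / ΣN.**
- Table XIII rates and counts: (662×84.0 + 1,175×80.5 + 901×94.8 + 649×83.6 + 958×83.8) / 4,345 = 370,147.1 / 4,345 = 85.19%.
- Table XIII rates, Table VI limbs: 361,510.1 / 4,247 = 85.12%.
- Table XIII rates, Table VI patients: 335,485.2 / 3,943 = 85.08%.
- Table IV: the 68 printed Ns sum to 3,943, which is the patient total. The 67 series that report patency (N = 3,927) give 85.48%.

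Rounding does not close the gap. With every Table XIII rate raised by 0.05 points, the largest mean is 85.24%, and at least 85.65% is needed to print as 85.7%. With the Table XIII counts, the other four categories average 82.67%, so 85.7% needs a non-thrombotic weight of (85.7 − 82.67) / (94.8 − 82.67), or about 25%. The three sets of counts give that group 20.0–20.7%.

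**4. Power at those rates**, N = 160 with pass at 131 or more, safety held at 0.9233:

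| Planning rate | Source | Effectiveness | Overall (product) | Overall (lower bound) |
|---|---|---|---|---|
| 85.08% | XIII rates, VI patients | 89.2% | 82.3% | 81.5% |
| 85.12% | XIII rates, VI limbs | 89.5% | 82.6% | 81.8% |
| 85.19% | XIII rates and counts | 89.9% | 83.0% | 82.2% |
| 85.48% | IV, by patients | 91.7% | 84.7% | 84.0% |
| 85.70% | as stated | 92.9% | 85.8% | 85.2% |

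Effectiveness power reaches 92% at a rate of about 85.54%. Overall power (product) reaches 84% at about 85.36%.

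**5. The goal.** 85.1–85.5% less 10 points is 75.1–75.5%, which is still taken down to 75%.

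**The case against.** The strongest reply is that the appendix does not show which number is at fault. Table XIII is by limb and the Ns in Table IV are patients, so 85.48% is not the quantity that Table XIII reports. Limb counts per series are not printed. If the extra limbs in Table VI may fall on any series, with none more than doubled (an assumption), a limb-weighted Table IV mean could lie anywhere from 84.0% to 86.3%, which includes 85.7%. The category rows are also open to doubt. For the same eight mixed post- and non-thrombotic series, Table IV gives 85.5% by patients and Table XIII prints 83.8%. Table IV category means weighted by the Table XIII counts give 85.6%, at which effectiveness power would be 92.4%. This reply stands, and it limits the conclusion to a failure to reconcile.

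A second reply is that nothing in the design turns on the difference. That is also correct. The goal, the cut-off of 131 and the sample size are unchanged, enrolment is complete, and a shift of 0.2–0.6 points is small for a rate drawn mostly from retrospective series. It does not rescue a power statement worded as a floor.

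A reader might infer that overall power is nearer 80%, by counting all 200 subjects as evaluable for safety and only 160 for effectiveness. The documents plan on 193 and 160. With 200 for both endpoints (pass at 163 or more, and 15 or fewer events), overall power at the rates in question is 84.2–85.9%. The mixed scenario is therefore no basis for a lower figure.

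**Conclusion.** The point holds as a failure to reconcile. The printed tables give 85.1–85.5%, none of the printed weightings gives 85.7%, and the Table XIII counts differ from their total by 98 (4,345 − 4,247). At the planned 160 and 193 evaluable subjects, effectiveness power over that range is about 89–92%, below the stated floor of 92% at each of the four re-derived rates. Overall power is about 82–85%. It falls below the stated 84% for the Table XIII and Table VI weightings but not for patient-weighted Table IV. The 80% requirement is met at every rate, including on the lower bound (81.5%).

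A reader might go further and conclude that 85.7% is wrong, that the power calculation is wrong, or that the trial was underpowered. The documents support none of these. The limb-level data that would settle the rate are not shown, the calculation reproduces exactly, and the overall requirement is met. The overall figures assume independent endpoints unless marked as the lower bound, and they keep the 5.6% safety rate as stated.

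**What to change.** Reconcile Tables IV and XIII with the limb-level data, including the Table XIII row counts and the mixed post- and non-thrombotic rate. Then either state the weighting that yields 85.7% or correct the figure wherever it is used: protocol 5.1.1, 14.1.1 and Appendix A, and SAP 6.1, 6.3 and 7.9.1.2. In protocol 14.2 and SAP 6.3, replace the two power floors with the range over planning rates of 85.1–85.7%: effectiveness about 89–93% and overall about 82–86%, at 160 and 193 evaluable subjects. Leave the sample size, the 75% goal and the success rule unchanged.

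The cost is a text correction and a check against the literature extraction file. The stated power becomes slightly less favourable, and no analysis or decision changes.

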### 14.1.2 Performance Goal: Primary Safety Endpoint

The study's primary safety endpoint is defined as a composite of all-cause death occurring post-procedure, clinically significant (i.e. symptomatic, confirmed by CT pulmonary angiography) pulmonary embolism, major bleeding complication (procedural), stent-migration and stent thrombosis confirmed by imaging as assessed by core laboratory within 30 days of the index procedure. The review of the literature that provided results on these endpoints suggests an expected rate of 5.6% (see **Appendix A Scientific Literature Search**). It should be noted that considerably less data, compared to primary patency, was found for the components of this composite endpoint.

Therefore, due to the greater uncertainty, a relatively larger margin of indifference was used of 6.8% giving a performance goal of 12.5%. Formally, the null and alternative hypotheses to be tested appear below:

$$H_0: P \geq PG$$

$$H_A: P < PG$$

where P is the primary safety endpoint at 30 days in the study population and PG is the performance goal.

## 14.2 Sample Size Calculation

**Primary Effectiveness:** Using the assumptions above on the performance goal and anticipated outcome, we assume desired power of at least 92% under difference testing relative to the performance goal at a one-sided alpha of 0.025. The resulting evaluable sample size required is then 160 subjects using exact binomial test for a single proportion. Accounting for attrition during follow-up, the sample size is augmented by 20% to 200 subjects. Every effort will be made, however, to minimize loss to follow-up.

**Primary Safety:** Using the assumptions above on the performance goal and anticipated outcome, we assume desired power of at least 92% under difference testing relative to the performance goal at a one-sided alpha of 0.025. The resulting evaluable sample size required is then 193 subjects using exact binomial test for a single proportion. Accounting for attrition during follow-up, the sample size is augmented by 3.5% to 200 subjects. Every effort will be made, however, to minimize loss to follow-up.

In summary, the overall power of the study is at least 84% while the effectiveness and safety performance goals are as follows:

**Table 15: Effectiveness and safety performance goals**

Endpoints	PGs
Primary Patency at 12 months	75%
MAE at 30 days	12.5%

## 14.3 Analysis Sets

The primary analysis set will consist of all subjects who were enrolled and had the Abre system introduced into the vasculature. In general, all analyses will be performed using all evaluable subjects for primary effectiveness and safety analyses (evaluable subject definitions provided below).

The PMA primary analysis will occur when all 12-month follow-up data have been collected.

For the primary effectiveness endpoint, subjects will be included in the primary analysis when:

- a) the subject experiences at least one clinically-driven target lesion revascularization within 390 days; or
- b) the subject has occlusion or restenosis  $\geq 50\%$  of the stented segment of the target lesion confirmed by core laboratory at 12 months visit; or
- c) the subject has at least 330 days follow up without an event in the primary effectiveness endpoint.

For the primary safety endpoint, subjects will be included in the primary analysis when:

- a) the subject experiences at least one of the primary safety composite events within 30 days; or
- b) stent-migration and stent thrombosis confirmed by imaging as assessed by core laboratory at 30-day visit; or
- c) the subject has at least 23 days of clinical follow up without an event in the primary safety endpoint.

Secondary analyses for primary safety endpoint will be conducted on all implanted subjects in whom the denominator for the primary safety endpoint will be the number of implanted subjects who had sufficient follow up (at least 23 days for 30-day visit) plus any subjects who had an event prior to the 30-Day Follow-Up visit.

One interim analysis will be performed on safety for the DSMB. The interim analysis is planned when 30-day follow-up data have been obtained on 30 subjects. The interim analysis does not permit early stopping for effectiveness and therefore no alpha-spending or other adjustment to the study's statistical hypotheses is required. The DSMB Charter may specify additional safety analyses.

Additional exploratory analyses of the data may be conducted as deemed appropriate.

## 14.4 Statistical Method

### 14.4.1 ABRE Pivotal Study Phase

The primary patency rate is calculated as the number of subjects without loss of primary patency divided by the number of subjects having evaluable primary endpoint data for primary patency rate at 12 months. The 12-month patency rate and lower limit of the 97.5% one-sided confidence interval will be reported. The primary effectiveness objective will be considered to be met if the lower limit of the 97.5% one-sided confidence interval of the 12-month patency rate is above 75%. For analysis of the imaging component of primary patency, if a subject has both a valid venogram and DUS during the 12-month follow-up period then the venogram will be used. If no venogram is available, then the DUS will be used.

The primary safety failure rate is calculated as the number of subjects who had an event prior to the milestone visit divided by the number of evaluable subjects who had sufficient follow up (at least 23 days for 30-day visit) plus any subjects who had an event prior to the milestone visit.

Primary safety failure rate and the exact one-sided 97.5% upper confidence limit (UCL) will be reported. The primary safety objective will be considered to be met if the exact one-sided 97.5% UCL is below 12.5%.

